4.9.4 Laboratory Data

4.9.4.1 Safety Laboratory Parameters

All laboratory data will be converted to SI units. The Safety Laboratory Data Standardization will be used to implement reference ranges and marked abnormalities for laboratory data where possible.

Summary statistics for the absolute and change from baseline values will be produced by visit for laboratory parameters.

Marked abnormalities will be summarized for laboratory parameters. Summaries by National Cancer Institute Common Terminology Criteria for Adverse Events (NCI-CTCAE) grade will also be produced for lab assessments, including shift tables from baseline to highest grade post-baseline.

Shift tables from baseline to highest NCI-CTCAE grade post-baseline will be produced for liver function laboratory tests.

Positive pregnancy results will be listed, as identified using the serum test results, where the data will be taken from CRF “pregnancy report” page.

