- ^g The DLQI, PGIC, and Skindex-29 should be completed before all other assessments during the study visit and prior to providing patient with any disease status information. The CGIC, where possible, should be completed prior to the completion of other non-PRO study assessments.
- ^h To be captured on the eCRF.

Handling and Reporting of Laboratory Safety Data

This document describes methods used to standardize laboratory safety data for analysis and reporting purposes and presents for laboratory parameters that are frequently assessed in Roche/Genentech studies the range of values and changes from baseline for each laboratory test beyond which a value might be clinically relevant.

Standardization Methods

In clinical trials, samples for a particular laboratory parameter may be analyzed by several laboratories often using different methods. This can result in values being reported in different units with different reference ranges. Thus, to make the values comparable for analysis and reporting purposes, the following standardization process is applied to the data.

Conversion of values to Système International (SI) units

Where applicable, laboratory test values were converted from the investigator reported units to Système International (SI) units.

Transformation of data

For those tests that use common methodologies, a 'Roche Standard Reference Range' (adopted from the New England Journal of Medicine [[Kratz and Lewandrowski 1998](#), [Kratz et al. 2004](#)]) was applied since their normal ranges show only slight variation between different laboratories. For other tests where different methodologies are used between laboratories, and thus the reference ranges differ widely, values were linearly transformed to a 'Roche Standard Reference Range' before analysis and reporting using the following formula ([Smith and Givens 1993](#)):

(1)

$$R_T = S_L + [(R_U - I_L) / (I_H - I_L)] * (S_H - S_L)$$

R_T	transformed value
R_U	untransformed value
I_L, I_H	investigator limits, low and high
S_L, S_H	reference limits, low and high

Note: Values for females (where there are sex-dependent reference ranges) were transformed to the male reference range by replacing I_L, I_H by the reference limits for females, and S_L, S_H by the reference limits for males.

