Baseline was defined as the last valid value within a window specified by the project team (e.g., 30 days) before starting trial treatment. If no baseline was available, then the midpoint of the Standard Reference Range was used.

For crossover studies or parallel studies where treatment interruption longer than a specified period is of clinical significance: In general, if the wash-out interval was sufficient between 2 consecutive treatment periods, the user could derive a new baseline for the later of the 2 consecutive periods, as agreed within the project team.

NOTE: For calculating means and mean changes over time, missing values were not included. If no baseline was available, no change from baseline was calculated.

Table 1 Overview of Laboratory Parameters for Safety Reporting

Laboratory Test Class Laboratory Test	Specimen	SI Unit	Significant Decimals	Standard Reference Range ^{f, g, h}	Marked Reference Range	Direction of Change	Clinically Relevant Change from Baseline
HEMATOLOGY							
Hematocrit (PARAMCD = HCRIT)	Blood	fraction of 1	2	M 0.41–0.53 F 0.36–0.46 ^a	0.31–0.56	Increase Decrease	≥15% ≥15%
Hemoglobin (PARAMCD = HGB)	Blood	g/L	0	M 135–175 F 120–160 ^a	110–200	Increase Decrease	≥15% ≥15%
Leukocytes (WBC) (PARAMCD = WBC)	Blood	10 ⁹ /L	1	4.5–11.0	3.0–18.0	Increase Decrease	≥30% ≥30%
Platelets (PARAMCD = PLATE)	Blood	10 ⁹ /L	0	150–350	100–550	Increase Decrease	≥50% ≥30%
Mean corpuscular hemoglobin (MCH) (PARAMCD = MCH)	Blood	pgl	1	26.0–34.0	21.2–40.2	Increase Decrease	≥15% ≥15%
Mean corpuscular hemoglobin concentration (MCHC) (PARAMCD = MCHC)	Blood	g/L	0	310–370	260–430	Increase Decrease	≥15% ≥15%
Mean corpuscular volume (MCV) (PARAMCD = MCV)	Blood	fL	0	80–100	66–115	Increase Decrease	≥15% ≥15%
Erythrocytes (RBC) (PARAMCD = RBC)	Blood	10 ¹² /L	2	M 4.50–5.90 F 4.00–5.20 ^a	3.80–6.10	Increase Decrease	≥15% ≥15%

Laboratory Test Class Laboratory Test	Specimen	SI Unit	Significant Decimals	Standard Reference Range ^{f, g, h}	Marked Reference Range	Direction of Change	Clinically Relevant Change from Baseline
DIFFERENTIALSⁱ							
Bands (PARAMCD = BANDS)	Blood	10 ⁹ /L	2	0–0.70	0–1.40	Increase	≥30%
Bands (PARAMCD = BANDSF)	Blood	fraction of 1	2	0–0.10	0–0.15	Increase	≥30%
Basophils (PARAMCD = BASOS)	Blood	10 ⁹ /L	2	0–0.20	0–0.40	Increase	≥100%
Basophils (PARAMCD = BASOSF)	Blood	fraction of 1	2	0–0.03	0–0.06	Increase	≥100%
Lymphocytes (PARAMCD = LYMPH)	Blood	10 ⁹ /L	2	1.00–4.80	0.70–7.60	Increase Decrease	≥30% ≥30%

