
NOTE: Laboratory tests in bold are proposed as the minimal standard. All other tests are optional.
 
^a For reporting and analysing, the data for females are linearly transformed to the Reference Range for males according to formula (1).
 
^b For reporting and analyzing, the data are linearly transformed to the Reference Range according to formula (1).
 
^c For reporting and analysing, the data are linearly transformed to the Reference Range according to formula (1). To prevent transformed values becoming negative, the investigator lower limit is replaced by zero.
 
^d To be done if dipstick is positive and microscopic examination needed for specific quantitation/confirmation.
 
^e Specific gravity is a measurement of solute load in the urine. It is increased markedly by both proteinuria and glycosuria. A value >1.030 in the absence of proteinuria or glycosuria is most commonly caused by radiographic contrast. In volume depletion specific gravity is usually >1.020. A fixed value of 1.010 (isosthenuria) is characteristic of chronic renal impairment. A fixed value of 1.000–1.005 occurs in diabetes insipidus. Specific gravity has an important influence on urine microscopy because cells lyse more rapidly in dilute urine, which may lead to considerable inaccuracies in quantitation of cells. Cells swell and rupture in dilute urine and shrink in concentrate urine. Casts are rarely seen at low urine osmolality (Johnson and Feehally 2000). Conclusion: increase or decrease in urine specific gravity clinically relevant in context with other parameters from urinalysis.
 
^f Kratz and Lewandrowski 1998.
 
^g New England Journal of Medicine 1992 SI conversion guide.
 
^h Kratz et al. 2004.
 
ⁱ Harrison's Textbook of Internal Medicine.
							

References

Harrison's Textbook of Internal Medicine. Absolute Values of Differentials

New England Journal of Medicine. 1992 SI conversion guide

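### The laboratory annex rescales women's haemoglobin, haematocrit, red cells and uric acid to the male range, so the tabulated values are not those measured; whether CTCAE grades are affected is left open

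*SAP*

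**What the plan says.** The annex, Handling and Reporting of Laboratory Safety Data, stands at the end of the SAP document. Under Transformation of data it gives a linear formula (1) and adds: "Values for females (where there are sex-dependent reference ranges) were transformed to the male reference range". Footnote a of its Table 1 repeats the rule with its scope: "For reporting and analysing, the data for females are linearly transformed to the Reference Range for males according to formula (1"). The footnote marks haematocrit, haemoglobin, red cells, uric acid and creatine kinase. Creatine kinase is not in this trial's chemistry panel (protocol 4.5.6).

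SAP 4.9.4.1 calls on the sponsor's laboratory standardization for reference ranges and marked abnormalities, where possible. In separate sentences it plans two further outputs:

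- "Summary statistics for the absolute and change from baseline values will be produced by visit for laboratory parameters"
- "Summaries by National Cancer Institute Common Terminology Criteria for Adverse Events (NCI-CTCAE) grade will also be produced for lab assessments"

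It does not say whether either output uses rescaled or measured values.

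**The concern.** Rescaling to a common range is sensible for a flag that only asks where a value lies relative to its normal limits. It is wrong for a reported concentration, because a reader of a by-visit table takes the figure in g/L to be what the laboratory measured. It also disturbs a percentage change, because adding a constant alters the denominator.

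Anaemia is a named risk of MMF (protocol 5.1.2), and haemoglobin is one of the tests to be watched closely (protocol 5.1). Summary statistics, minima and maxima for women, and any mean pooling the sexes, would be off by a known amount that the table does not show. If the grade tables use the same variable, the reported incidence of low-haemoglobin grades in women would be too low.

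**Working it through.** **Inputs** (annex Table 1): haemoglobin "M 135–175 F 120–160" g/L, marked range 110–200, clinically relevant change at least 15%; haematocrit "M 0.41–0.53 F 0.36–0.46"; red cells "M 4.50–5.90 F 4.00–5.20" × 10¹²/L; uric acid, men 150–480 and women 90–360 µmol/L.

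**Formula (1):** transformed = S_L + [(measured − I_L)/(I_H − I_L)] × (S_H − S_L), with the female limits as I and the male limits as S.

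**The annex's own claim first.** For haemoglobin, 120 maps to 135 + 0 = 135, and 160 maps to 135 + 40 × (40/40) = 175. Low, normal and high status is preserved, as the annex says.

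**By-visit values and changes in women**

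| Test | Slope (multiplies changes) | Transformed value | Example |
|---|---|---|---|
| Haemoglobin | 40/40 = 1.00 | x + 15 | 80 → 95 |
| Haematocrit | 0.12/0.10 = 1.20 | 1.20x − 0.022 | 0.30 → 0.338 |
| Red cells | 1.4/1.2 = 1.17 | 1.167x − 0.167 | 4.00 → 4.50 |
| Uric acid | 330/270 = 1.22 | 1.222x + 40 | 360 → 480 |

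The 80 g/L in the example is the protocol's haemoglobin exclusion limit (8.0 g/dL, protocol 4.1.2). With slope 1, haemoglobin changes in g/L are correct. Uric acid is inflated.

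**Marked low haemoglobin.** A flag needs a transformed value below 110, which is a measured value below 110 − 15 = 95, and a fall of at least 15%. Take a woman who goes from 110 to 93 g/L.

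- As measured: 17/110 = 15.5%.
- Transformed: 125 to 108, 17/125 = 13.6%.

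The value is outside the marked range (108 < 110), yet the change criterion fails and no flag is raised.

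**How far this reaches.** For baseline b and later value v, the measured criterion is v ≤ 0.85b. The transformed criterion is v + 15 ≤ 0.85(b + 15), that is v ≤ 0.85b − 2.25. The two can disagree only if 0.85b − 2.25 < 95, so only for b below 97.25/0.85 = 114.4 g/L, and then only in a band at most 2.25 g/L wide. At higher baselines, falling below 95 already exceeds 15% on either scale.

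**Grades.** Neither document gives the CTCAE cut-offs, so only the general form can be shown: if grades use transformed values, a boundary of C g/L acts at a measured C − 15 in women.

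**The case against.** The strongest reply is about scope. SAP 4.9.4.1 names the standardization only for reference ranges and marked abnormalities. The sentences on by-visit summaries and on grades do not invoke it, the annex never mentions grading, and it is a generic sponsor text written in the past tense. This stands for the grades. It does not clear the by-visit values, because footnote a covers reporting in general and the annex also sets rules for calculating means and mean changes.

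The shift is also partly deliberate. The marked-low limit lies 25 g/L below the lower normal limit in both sexes (135 to 110 in men; 120 to 95 measured in women), so comparing transformed values with that range amounts to a sex adjustment. That stands, and it is why this one use should stay. It does not justify the diluted percentage change.

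A reader might infer three stronger points, and the documents support none of them:

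- **That the grade tables will understate anaemia in women.** This follows only if grades are derived from transformed values, which is not stated. Without the cut-offs or a haemoglobin distribution, no size can be given.
- **That the comparison between arms is biased.** The rule is identical in both arms, and nothing shows a bias.
- **That anaemia would be missed in care or in safety reporting.** The rescaling acts on analysis and reporting, not on site results. Clinically significant abnormal values are reported as adverse events (protocol 5.3.5.5), graded under CTCAE (protocol 5.3.3) and summarised by grade (SAP 4.9.2). That route is untouched.

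**Conclusion.** Wrong as written, within limits. If the annex is followed, women's by-visit haemoglobin is 15 g/L above the measured value. Haematocrit, red cell and uric acid values are also altered, with changes multiplied by 1.20, 1.17 and 1.22. Haemoglobin changes in g/L are right. The marked-low haemoglobin flag can be missed in women, but only for baselines below about 114 g/L and within a narrow band. The effect is on reported levels and incidence, in the same way in both arms.

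This rests on two readings: that the annex is the standardization named in SAP 4.9.4.1, and that its reporting scope covers the by-visit tables. For CTCAE grades the plan is ambiguous: grades could understate anaemia in women, but the text does not establish that they will.

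**What to change.** State in SAP 4.9.4.1 that the following use untransformed SI values, with sex-specific normal limits: absolute values; changes from baseline, including the percentage change used to define a marked abnormality; and CTCAE grades. State also that the female-to-male transformation is used only to compare a value with the marked reference range.

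Confining the transformation to marked abnormalities as a whole would not be enough, because the diluted 15% criterion sits there.

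The cost is small: a short addition to the SAP, use of the untransformed variable in programming, and a departure from the sponsor's standard display. If the sponsor already intends this, the statement only removes the ambiguity.
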